5.2 Outcome Variables

5.2.1 Primary Outcome Variables

Primary Outcome Measure:

1. Engagement Activity

Total minutes logged on the mobile application will be evaluated between the two groups using the mobile application.

[Time Frame: through the completion of the study, on average 4 months.]

2. Pain Severity

A comparison within groups change of pain severity measured by the Brief Pain Inventory-Short Form. Respondents rate items on a 0-10 scale to indicate the pain severity and interference, and the total score is the mean of each subfactor. The higher the score indicates more severity and interference of pain.

[Time Frame: through the completion of the study, on average 4 months.]

3. Pain Interference Index

A comparison within groups change of pain interference measured by the Pain Interference Index Scale. Respondents rate items on a 0-6 scale to indicate how much pain has interfered with various activities, and the total score is the mean of the six items. Where 6 indicates high interference.

[Time Frame: through the completion of the study, on average 4 months.]

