5.3.2 Eligibility Criteria/Vulnerable Populations

Patients will be included in the study if they meet the following inclusion criteria:

- 1) adults older than age of 18
- 2) diagnosis a diagnosis of NF1;
- 3) permanently reside in the United States and
- 4) have pain interference aggregate scores of three or more in the last two weeks using the Brief Pain Inventory-Short Form (BPI-SF) scale.

Patients will be excluded if they: 1) have an undiagnosed case of NF1; 2) have documented major co-occurring psychiatric disease; 3) have moderate to severe cognitive deficits; or 4) have depression assessed using the Patient Health Questionnaire (PHQ-9) or anxiety assessed using the Generalized Anxiety Disorder scale (GAD-7) greater than or equal to the appropriate thresholds (10=mild major depression; 5=mild severe anxiety).

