6.4 Statistical Method

6.4.1 Statistical Design

Statistical procedures and models have been selected according to the research questions being investigated and the types of data available. We will use $\alpha < .05$ but will use appropriate corrections for multiple tests. Statistical analyses will be conducted by principal investigator using SPSS, SAS, or R with consultation from the coinvestigators. Using logistic regression for categorical and ANOVA for continuous measures, we will conduct preliminary analyses of the adequacy of the randomization procedure, the comparability of baseline measures across conditions, and the possible need for covariates in the analyses of treatment outcome data.

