6.4.3.1 Primary Analyses

For the primary first outcomes: Can we identify the feasibility of the *iCanCope-NF* program? This will be evaluated using general linear model of count data (logins, dropout rates, completion of outcome measures, engagement activity, (i.e. user and aggregate levels). Additionally, the proportional changes will be evaluated using an ANOVA. Due to potential missing data assumptions, a Cox regression will evaluate for differences in relationship between pre-and post. For second primary outcome: what are perceptions regarding intervention acceptability and satisfaction; and what are the levels of engagement with the intervention? Aggregate values will be summed and standardized through a (z-score analysis) to ensure equal representation of groups. Lastly, for the levels of engagement and number of activities tried/TSN exercises will be examined with linear and non-linear Mixed-effects Models (LMM) with autoregressive 1 correlation structure (AR1) to test between conditions, while allowing for intra-participant serial correlation and unequal variance and covariance structure across time.

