6.4.3.2 Secondary Objectives Analyses, if applicable

Secondary analyses will explore three research questions: (1) Does smartphone program (*iCanCope-NF*) compared with control condition lead to differences in pain and pain-related activity limitations, sleep functioning, emotional functioning (depression, anxiety), pain catastrophizing, self-efficacy, knowledge, psychological flexibility immediately post-treatment (T2)? This will be evaluated by incorporating an estimating equation approach to understand the differences in scores and using a sequential multilevel logistic regression models to estimate the independent and combined effects of proposed time-varying (contextual) variables on the probability of pain levels. We will also test interaction effects between stable/trait-level participant characteristics and contextual variables. (2) Does the *iCanCope-NF + CM* increase the usage of the *iCanCope-NF* program as compared to *iCanCope-NF* without CM, and do their corresponding levels of pain and pain-related activity decrease? This will be evaluated between the two intervention groups and using the difference in nominal data sets, and simple qualitative analyses. (3) Do individuals with NF1 utilize the MBAA more readily because they are on the mobile application? To assess the moderation effect, we will include an interaction term for each separate moderator variable and key predictor of interest (two-way interaction between moderator and group for cross-sectional analysis and three-way interaction between moderator, group and time for longitudinal analysis) in the regression models and test its significance using Wald t-test.

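### The ANOVA of proportional changes names no variable, no suitable primary model is given for the two pain outcomes, and no analysis prespecifies the baseline score as a covariate

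*Combined protocol and SAP*

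**What the plan says.** The feasibility paragraph of section 6.4.3.1 (repeated in 6.4.3) has three consecutive statements. The first concerns app use and retention: "This will be evaluated using general linear model of count data (logins, dropout rates, completion of outcome measures, engagement activity". The second is "Additionally, the proportional changes will be evaluated using an ANOVA". The third says that, because of possible missing data, "a Cox regression will evaluate for differences in relationship between pre-and post".

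Section 5.2.1 lists three primary outcomes, two of them pain scores. For severity it gives "A comparison within groups change of pain severity measured by the Brief Pain Inventory-Short Form", scored 0 to 10. For the Pain Interference Index it says "Respondents rate items on a 0-6 scale to indicate how much pain has interfered with various activities", again as a within-group change.

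Section 6.4.3.2 takes up the comparison of the app with control at T2 on pain, sleep and emotional functioning, as a secondary question: "This will be evaluated by incorporating an estimating equation approach to understand the differences in scores". Multilevel logistic models are added. It does not mention the baseline score as a covariate.

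Section 6.4.1 leaves to preliminary analyses "the possible need for covariates in the analyses of treatment outcome data", and section 6.4.4 on covariates is marked not applicable. Eligibility (section 5.3.2) requires participants to "have pain interference aggregate scores of three or more in the last two weeks using the Brief Pain Inventory-Short Form (BPI-SF) scale".

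**The concern.** A statistician could not run the second statement as written, because it does not say what changes, relative to what, or between which visits. That matters because section 6.4.3.1 is where one looks for the analysis of the primary pain outcomes, and it contains only two methods worded in terms of change or pre and post. One is this ANOVA. The other is a Cox regression, which needs an event and a time to it, and a change in a questionnaire score supplies neither. An analyst looking for the primary pain analysis could therefore settle on percent change.

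Percent change divides by the baseline. It does not exist when the baseline is zero, and a participant with a low baseline can dominate an arm's mean and variance. The eligibility floor is on BPI interference. Neither BPI severity nor the Pain Interference Index has a floor. Section 6.4.5 adds to the problem by coding missing values as zero: a missing follow-up would become a 100% improvement, and a missing baseline would make the ratio undefined.

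What is at stake is power to see a pain difference with 36 per arm, and a result that may depend on a few low-baseline participants.

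**Working it through.** **1. Which variable?**
- App logins and minutes have no pre-treatment value, since access follows randomisation (sections 6.1.1 and 6.1.4). A change from baseline cannot be formed for them, though a change over the 8 weeks can.
- Dropout and completion are proportions, so the sentence could mean a change in proportions.
- Questionnaires are measured at intake, discharge and follow-up (sections 6.2.1 and 6.3.6), so percent change from baseline can be formed for them.

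The text does not choose among these.

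**2. Inputs.** From the documents: 36 per group; alpha 0.05 (taken as two-sided, which is not stated); scales 0 to 10 and 0 to 6; entry at BPI interference of 3 or more. There is no plan figure to reproduce, because no effect, SD, correlation or target power is given. Everything else below is assumed.

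**3. Closed-form anchor.** Take two arms of 36 and a 1-point effect with SD 2, so d = 1/2 = 0.5. Power is approximately Φ(d/m × √(36/2) − 1.96), with m = √(2(1−r)) for raw change and m = √(1−r²) for ANCOVA.
- r = 0.5, raw change: m = 1; 0.5 × 4.243 = 2.121; power 56%.
- r = 0.5, ANCOVA: m = 0.866; 0.577 × 4.243 = 2.449; power 69%.
- r = 0.7, raw change: m = 0.775; 2.739; power 78%.
- r = 0.7, ANCOVA: m = 0.714; 2.971; power 84%.

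**4. Percent change by simulation.** Two arms of 36, 1-point effect, severity clipped to 0 to 10 and rounded to 0.25, zero baselines dropped from percent change.

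| Baseline assumption | r | Percent change | ANCOVA | Loss (points) |
|---|---|---|---|---|
| Mean 5, SD 2, unselected | 0.5 | 36.4% | 66.9% | 30.5 |
| Same | 0.7 | 57.3% | 82.4% | 25.1 |
| Same, selected on interference ≥ 3 (mean 4.5, SD 2, correlation 0.7 with severity) | 0.5 | 51% | 67% | 16 |
| Same, selected | 0.7 | 73% | 84% | 11 |
| Mean 6, SD 1.5 | 0.5 | 74% | 89% | 15 |
| Mean 6, SD 1.5 | 0.7 | 93% | 97% | 4 |

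In the first two rows raw change gave 54.7% and 75.6%, between the other two methods. Independent repeats moved the figures by no more than about 2 points.

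**5. Three-arm check.** Overall F test, 3 × 36, additive effect of 0.6 SD in both app arms, no selection on interference, r = 0.3 / 0.5 / 0.7.
- BPI severity (mean 5, SD 2): percent change 34 / 49 / 75%, ANCOVA 78 / 86 / 96%.
- Pain Interference Index (mean 3, SD 1.5): 29 / 42 / 68% against 77 / 85 / 96%.
- BPI interference with its floor of 3 (mean 5.5, SD 1.8): 64 / 77 / 94% against 78 / 85 / 96%.

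The first two lines ignore selection at entry, so I treat them as upper sensitivity figures. The third shows how a floor shrinks the loss.

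**6. Zero baselines.** In the unselected case about 0.75% of severity baselines are zero: 108 × 0.0075 = 0.8 participants per trial, and 1 − 0.9925^108 = 56% of trials have at least one. With selection on interference the share is about 0.05%: 108 × 0.0005 = 0.05 participants, and 1 − 0.9995^108 = 5% of trials. Most of the power loss therefore comes from low, nonzero baselines.

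**The case against.** A reader might infer that the plan commits the pre-post questionnaire outcomes to a percent-change ANOVA. The documents do not say so. The sentence sits in the feasibility paragraph, straight after logins, dropout and completion. The words about pre and post belong to the next sentence and to a different method. Nor can the feasibility variables be ruled out for want of a baseline: engagement can change over the 8 weeks, completion is observed at intake and later, and a change in proportions is a natural reading after dropout rates. The zero-baseline and power arguments do not apply to those readings. This part of the objection stands, so the point can only be conditional.

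A second objection is that section 6.4.3.2 already assigns the app-versus-control pain comparison at T2 to estimating equations. That is correct, and any fix must respect it. But that analysis is labelled secondary, states no baseline adjustment, and leaves the primary pain outcomes of section 5.2.1 without a suitable model of their own.

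A third is that a large power loss rests on favourable inputs. This also stands in part. The largest two-arm loss ignores selection on interference, and it falls by roughly half once selection is assumed. An observed zero cannot occur on BPI interference at entry, but that scale is the entry criterion. The primary interference outcome is the Pain Interference Index, which has no floor.

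**Conclusion.** The point holds in conditional form. Two parts come directly from the text: the quantity to be analysed is not identified and section 6.4.3.1 gives no suitable model for the two primary pain outcomes; and no analysis prespecifies the baseline score as a covariate.

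The third part depends on meaning. If percent change in BPI severity or the Pain Interference Index is intended, it is undefined at zero and less efficient than a baseline-adjusted model. For severity, under the two-arm assumptions above, the loss is about 11 to 30 points in most scenarios and about 4 where power is already above 90%. The size depends on the baseline mean, the SD, the correlation and selection at entry, none of which the documents give. The direction does not: ANCOVA had more power than percent change in every scenario tried. An unconditional claim that the trial loses much of its power, or that zero baselines will be common, is not supported.

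**What to change.** In sections 6.4.3, 6.4.3.1 and 6.4.3.2:

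- State that pain severity, the Pain Interference Index and the other questionnaire scores will be compared between arms on the T2 score, with the baseline value of the same score as a covariate. This may be ANCOVA, or the estimating-equation model of section 6.4.3.2 with baseline added. Choose one, so that a single method covers this comparison, and align the within-group wording of section 5.2.1 with it.
- Report percent change descriptively only.
- If the ANOVA sentence is meant for dropout or completion proportions, keep it and name those variables and the time points. Otherwise remove it.
- Enter the baseline score in section 6.4.4, so that it does not depend on a preliminary look at the data.

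The cost is SAP wording. The baseline scores are already collected, and no extra participants, visits or measures are needed.

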5.2.2 Secondary and Exploratory Outcome Variables (if applicable)

Secondary Outcome Measures:

1. Treatment Services Review what are perceptions of satisfaction across groups exposed to the iCanCope mobile application using an The Treatment Services Review (TSR) [Time Frame: through the completion of the study, on average 4 months.]
2. Anxiety comparison within change of generalized anxiety measured by the generalized anxiety disorder scale (GAD-7). After reading each statement, one of four choices are provided and respondents can select one response (1=not at all sure, 2=several days, 3=over half days, 4=nearly every day). Each column is then added, and a total score is obtained, with scores falling into four levels of anxiety, including minimal (1-4), mild (5-9), moderate (10-14), and severe (15-21)[Time Frame: through the completion of the study, on average 4 months.]

3. Sleep functioning comparison within change of sleep quality measured by the PROMIS Sleep inventory. The higher the total score, the more severe the symptom. Total scores less than 24 suggest no to slight sleep disturbance, 24-28 suggest mild disturbance, 29-38 moderate disturbance, and greater than 38 severe sleep disturbance [Time Frame: through the completion of the study, on average 4 months.]
4. Short Form/Quality of Life the Short form survey 20- will measure quality of life across 8 subscales on respondent burden (Physical Functioning, Role-Physical, Bodily Pain, General Health, Vitality, Social Functioning, Role-Emotional, and Mental Health). Scores were transformed linearly to 0-100 scales, with 0 and 100 assigned to the lowest and highest possible scores, where high value indicated better functioning. [Time Frame: through the completion of the study, on average 4 months.]

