6.2 Assessments

6.2.1 Efficacy

All psychometric measures (see appendix) will be evaluated at intake, discharge, follow-up. All of these measures have evidence of reliability and validity in adults in this age range and include target specific measures of NF1 have recommended in previous trials. The **primary research** question is what is the feasibility of the *iCanCope-NF* program? We define feasibility as (1) rates of accrual and dropout, daily logins, engagement, and outcome measures completed and (2) perceptions regarding intervention acceptability and satisfaction; and what are the levels of engagement. logins, with the intervention? The **secondary questions** are: (1) how does the *iCanCope-NF* program compare with the control condition in differences of pain and pain-related activity limitations, sleep functioning, emotional functioning (depression, anxiety), opioid usage, pain catastrophizing, self-efficacy, respondent burden (i.e. Physical Functioning, R, Vitality, Social Functioning, Role-Emotional, and Mental Health), and psychological flexibility immediately post-treatment (T2), (2) does the *iCanCope-NF + CM* increase the engagement of the *iCanCope-NF* program as compared to *iCanCope-NF* without CM, and do their corresponding levels of pain and pain-

related activity decrease with CM?, and (3) do individuals with NF1 utilize the MBAA to help reduce pain symptoms? We hypothesize that by customizing and including MBAA to the program for adults with NF1, that individuals who engage regularly as seen through Analytics Platform for Evaluating Effective Engagement (APEEE) application, will acquire new sets of skills to facilitate pain management, while pain as reported with the Brief Pain Inventory will decrease.

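### Pain, app usage and satisfaction are ranked differently across 5.2, 6.2.1 and 6.4.3, and the promised multiplicity correction names no method or family, so the rank, analysis and threshold of the engagement and pain results are not fixed in advance

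*Combined protocol and SAP*

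**What the plan says.** **Pain.** Reducing pain severity and interference is the primary objective (4.2), and secondary objectives are entered as not applicable (4.3). Section 5.2.1 lists pain severity on the Brief Pain Inventory and the Pain Interference Index as primary outcomes 2 and 3, each as a change within groups. Section 6.2.1 instead makes feasibility the primary research question and puts pain, app versus control, in secondary question 1. Section 6.4.3.1 (Primary Analyses) does not mention pain. Section 6.4.3.2, introduced by "Secondary analyses will explore three research questions", takes it up as question 1.

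**App usage.** Primary outcome 1 in 5.2.1 is "Total minutes logged on the mobile application will be evaluated between the two groups using the mobile application". Section 6.4.3.1 models engagement "with autoregressive 1 correlation structure (AR1) to test between conditions". Whether contingency management (CM) raises use over the app alone is also secondary question 2 in both 6.2.1 and 6.4.3.2.

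**Satisfaction.** Secondary outcome 1 in 5.2.2 asks "what are perceptions of satisfaction across groups exposed to the iCanCope mobile application using an The Treatment Services Review (TSR". Section 6.2.1 counts satisfaction within its primary question, and 6.4.3.1 opens its second item with "For second primary outcome: what are perceptions regarding intervention acceptability and satisfaction; and what are the levels of engagement with the intervention".

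**Multiplicity.** Section 6.4.1 sets alpha at .05 and says the analysis "will use appropriate corrections for multiple tests". Section 6.4.3 repeats this. Neither names a procedure, a family of tests or an order of testing.

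**The concern.** An analyst who follows this plan cannot tell which results carry the primary claim. Pain is the stated objective but has no primary analysis. The CM-versus-app comparison has two ranks and two methods. A correction is promised, but there is no agreed list for it to act on.

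The significance threshold for the engagement and pain results, and in part the analysis that produces the p-value, could therefore be settled after the data are known. Section 3.2 makes a definitive trial depend on initial feasibility and preliminary impact, so what counts as a positive result here has consequences. Section 6.4.1 also has the principal investigator run the analysis, and 5.1.2 gives the research team a dashboard for monitoring engagement. That is a further reason to fix the rules in writing, although 7.5 says the routine monitoring reports withhold data that could influence the outcome.

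**Working it through.** The plan states no adjusted threshold, so there is no figure of its own to reproduce. The sample-size text (6.4.2) names no outcome, effect size, SD or power, so it does not show which comparison the trial was sized for.

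**Step 1: ranks and methods side by side.**

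| Item | Ranked primary | Ranked secondary | Analysis described |
|---|---|---|---|
| Pain severity and interference | 4.2; 5.2.1 (within-group change) | 6.2.1 and 6.4.3.2, question 1 (app versus control, T2) | None in 6.4.3.1; estimating equations and multilevel logistic models in 6.4.3.2 |
| App usage, CM versus app alone | 5.2.1, outcome 1; 6.4.3.1 | 6.2.1 and 6.4.3.2, question 2 | Mixed model with AR1 in 6.4.3.1; nominal-data comparison and qualitative work in 6.4.3.2 |
| Satisfaction | 6.2.1; 6.4.3.1 | 5.2.2, outcome 1 | Summed and z-scored in 6.4.3.1; no test stated |

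Section 6.4.3.1 does mention an ANOVA of proportional changes and a Cox regression on pre-post differences. Both follow a list of feasibility counts, and neither names a pain measure.

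**Step 2: what the open family does to the threshold.** Inputs: alpha 0.05 (6.4.1), assumed two-sided; a Bonferroni-type correction, also assumed; k tests in the family. The first-step threshold is 0.05/k.

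- The two outcomes that 6.4.3.1 numbers: 0.05/2 = 0.025.
- The three outcomes of 5.2.1, one test each: 0.05/3 = 0.0167.
- Section 5.2.1 read literally, with two within-group pain comparisons in each of three arms plus one engagement test: 2 × 3 + 1 = 7, and 0.05/7 = 0.0071.

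A smallest p-value of 0.020 would pass the first threshold and fail the other two. One of 0.012 would pass the first two and fail the third.

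**Step 3: what that means for a two-arm comparison.** With 36 per arm (6.4.2) and a normal approximation, the standardised difference detectable with 80% power is (z for 1 − α/2, plus z for 0.80) × √(2/36), where √(2/36) = 0.2357.

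- α = 0.05: (1.960 + 0.842) × 0.2357 = 0.66 SD
- α = 0.025: (2.241 + 0.842) × 0.2357 = 0.73 SD
- α = 0.0167: (2.394 + 0.842) × 0.2357 = 0.76 SD
- α = 0.0071: (2.690 + 0.842) × 0.2357 = 0.83 SD

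These apply to a comparison such as minutes between the two app arms, not to within-group changes.

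**The case against.** The strongest reply is that this is a pilot aimed at feasibility and preliminary effectiveness, with a definitive trial to follow, so strict familywise control is optional. That is fair as far as it goes. But the plan itself sets an alpha, promises a correction and tests between conditions. If no confirmatory testing is intended, it should say so.

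A second reply is that the primary item concerns levels of engagement and the secondary item the CM contrast. Section 5.2.1 rules this out, because its primary outcome is itself the comparison of the two app groups.

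A reader might also infer stronger conclusions that the documents do not support:

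- *That the conflicting labels cause the missing family.* Sections 6.4.1 and 6.4.3 name no method or family, so the gap would remain with consistent labels. The labels make it worse.
- *That moving satisfaction between lists shifts a threshold.* No test of satisfaction is described, so no such effect can be shown.
- *That one identical p-value passes under one section and fails under another*, for example by setting three tests in 5.2.1 (0.0167) against six in 6.4.3.1 (0.0083). The six come from counting every quantity mentioned, including satisfaction; 6.4.3.1 numbers only two outcomes, and 5.2.1 read literally gives seven tests. For usage, the two sections also use different methods, so the p-value itself may change.
- *That the error rate is 14% or 26%.* Those figures (1 − 0.95³ and 1 − 0.95⁶) are for uncorrected, independent tests. The plan promises a correction, and logins, engagement and activities tried are related measures.
- *That anyone means to choose a threshold afterwards.* The documents leave that possible; they do not show it.

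**Conclusion.** The point stands as an unresolved conflict in the current text. Pain and the CM-versus-app comparison each have two ranks and no single analysis, satisfaction has two ranks, and the correction has neither a method nor a family. The conflict over pain matters most, because it concerns the trial's only stated primary objective.

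The size can only be illustrated: first-step thresholds from 0.025 to 0.0071, and detectable differences from 0.73 to 0.83 SD for a two-arm comparison with 36 per arm. This range rests on an assumed two-sided Bonferroni-type correction and on readings of the outcome lists. It is not a measured inflation of the error rate. The plan should be corrected before analysis.

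**What to change.** Use one outcome list in 5.2, 6.2.1 and 6.4.3. The simplest is the 5.2.1 list, with one named analysis per outcome:

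- App minutes: iCanCope-NF + CM versus iCanCope-NF.
- Brief Pain Inventory severity: one named between-arm contrast against control, at a stated time point.
- Pain Interference Index: likewise.

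State that the between-arm pain contrasts replace the within-group wording of 5.2.1. Move the pain analysis into 6.4.3.1 and delete the duplicate usage comparison from the secondary questions in 6.2.1 and 6.4.3.2. Apply Holm at two-sided 5% to the three tests, with thresholds of 0.0167, 0.025 and 0.05 in order of p-value. Report satisfaction, logins, dropout, completion and activities tried as feasibility estimates with 95% confidence intervals.

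If the sponsor prefers feasibility as the primary question, as 6.2.1 has it, state instead that all comparisons are estimation-only with 95% confidence intervals, and align 4.2 and 5.2.1 with that.

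Either route needs wording only: no new data, visits or participants. The downside is that fewer results can be called significant. At the first Holm step the detectable difference is 0.76 SD, against 0.66 SD without correction.

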3.3.1 Potential Risks

The main risk associated with the study is the possibility that confidential information obtained during the study will be disclosed given the association of a medical disease and pain symptoms. Patient names and other identifying information do not appear on research records. For patients the iCanCope-NF must enter a unique id and passcode for access. All processes of obtaining information via Qualtrics, or iCanCope-NF will utilize proper data security methods to minimize any risks of for potential loss of confidentiality. **3.3.2 Potential Benefits**

We expect individuals with NF1 utilizing the iCanCope program to have decreased pain severity and interference if they regularly engage in the program. In addition, due to the added contingency management, we expect to see differences between the intervention groups (*iCanCope-NF* and *iCanCope-NF +CM*). By adding contingencies to increased

engagement the CM grouping should have more improvements in pain intensity and pain interference in addition to current iCanCope processes. If we demonstrate initial feasibility and preliminary impact a definitive RCT will be conducted.

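### Acceptability and satisfaction are to be analysed only as a z-score with no named reference; computed on the trial's own data, it cannot show whether satisfaction was low or high

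*Combined protocol and SAP*

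**What the plan says.** Section 6.2.1 makes feasibility the primary research question and counts acceptability and satisfaction as part of it. Section 6.4.3.1 puts the second primary outcome as "what are perceptions regarding intervention acceptability and satisfaction; and what are the levels of engagement with the intervention". The sentence that follows is the analysis: "Aggregate values will be summed and standardized through a (z-score analysis) to ensure equal representation of groups". Section 6.4.3 carries the same text. Neither says whether the mean and SD come from both app arms together, from each arm separately, or from an outside population.

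The plan then turns to engagement: "Lastly, for the levels of engagement and number of activities tried/TSN exercises will be examined with linear and non-linear Mixed-effects Models (LMM"). Engagement activity and logins are also among the count data for the first primary outcome, and section 5.2.1 lists a primary outcome in natural units: "Total minutes logged on the mobile application will be evaluated between the two groups using the mobile application".

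For satisfaction, section 5.2.2 names the Treatment Services Review and asks "what are perceptions of satisfaction across groups exposed to the iCanCope mobile application". It gives no score range or cut-off. Sections 6.4.3.2 and 6.4.3.3 add no analysis of satisfaction. No raw mean, proportion or confidence interval for it is planned anywhere.

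Section 3.3.2 states what follows from the pilot: "If we demonstrate initial feasibility and preliminary impact a definitive RCT will be conducted". Section 3.2 makes the definitive trial conditional in the same way.

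**The concern.** Whether users found the app acceptable is first of all a question about where their answers lie on the questionnaire's own scale. Standardising on the sample subtracts that location. What remains is each user's position relative to the other users, which says nothing about whether the group as a whole was content.

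Acceptability is part of feasibility by the plan's own definition, and the definitive trial depends on feasibility being shown. If the one stated analysis returns the same summary for a well-liked app and a disliked one, that component can neither support nor block the decision. Because the reference is unnamed, two analysts could also follow the text faithfully and report different answers to a primary question.

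**Working it through.** There is no stated sample size, power or error rate behind this point, so there is no plan figure to reproduce. The check is algebra, with a small numerical illustration.

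**Inputs.** From the plan: two app arms of 36 (section 6.4.2), so 36 + 36 = 72 users. Assumed, because the documents give no scale for the Treatment Services Review: normally distributed scores with SD 0.6, and true means of 1.5 (low) or 4.5 (high). A third scenario uses true means of 1.5 and 2.2 in the two arms. The algebra does not depend on these values.

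**Step 1: the mean.** With z = (x − m)/s, where m and s are the sample mean and SD, the mean of z is (m − m)/s = 0 for any data.

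**Step 2: a shift.** Add a constant c to every score. The mean becomes m + c and s does not change, so z = (x + c − m − c)/s = (x − m)/s. Every z-score stays as it was. Numerically, moving 72 scores up by 4.5 − 1.5 = 3 points changed no z-score by more than about 2 × 10⁻¹⁵, which is rounding error.

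**Step 3: the possible references.** Simulated results, 36 users per arm:

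| Scenario | Raw arm means | Pooled z: overall mean | Pooled z: arm means | Within-arm z: arm means | External z (assumed mean 3, SD 0.6): overall mean |
|---|---|---|---|---|---|
| Both low | 1.53, 1.39 | 0 | +0.14, −0.14 | 0, 0 | −2.56 |
| Both high | 4.45, 4.43 | 0 | +0.02, −0.02 | 0, 0 | +2.40 |
| Arms differ | 1.47, 2.17 | 0 | −0.49, +0.49 | 0, 0 | −1.97 |

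- *Pooled over both arms.* The level is gone. The comparison between arms survives in SD units: the raw difference of 2.17 − 1.47 = 0.70 appears as 0.49 + 0.49 = 0.98.
- *Within each arm.* The level and the difference between arms are both gone.
- *External reference.* The level survives. The documents name no such reference.

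**Step 4: the stated purpose.** A z-score rescales values. It changes neither how many people each arm contributes nor how the arms are composed, so it cannot equalise their representation. Arm sizes may well differ: the urn scheme in section 6.1.2 adjusts allocation probabilities without fixing the numbers, and under section 6.3.6 people who withdraw are not asked for the end-of-study survey. Standardising corrects neither.

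**Step 5: engagement.** The count model, the mixed model and total minutes are not described as standardised, and each can return results in natural units.

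**The case against.** Two stronger readings are tempting, and the documents support neither.

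A reader might infer that the z-score also disposes of the engagement results, since the sentence follows a question that covers both. It does not: engagement has the separate analyses quoted above. The word for levels in that question also attaches to engagement, while for satisfaction the plan asks about perceptions.

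A reader might also infer that no result could ever reveal low acceptability. That is too absolute. A pooled z-score can show one app arm below the other, and the wording of section 5.2.2 can be read as asking for just such a comparison. An external reference would preserve the level. The raw scores still exist, so the information can be recovered. Feasibility can also fail on accrual, dropout, logins or completion, which section 6.2.1 counts as well.

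Finally, it may be said that any report would include raw means as a matter of course. Perhaps so, but the plan does not say it, and a primary question should not depend on an unstated step.

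What stands is the narrow point. For satisfaction and acceptability the z-score is the only stated analysis, its reference is unnamed, and its stated reason is not something it achieves. An external reference is possible but unlikely to be meant, because that reason concerns the trial's own groups.

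**Conclusion.** The concern holds for acceptability and satisfaction only. If scores are standardised on the trial's own data, the loss of level is complete: the overall mean is exactly 0 whatever users reported. Pooled standardisation leaves the relative difference between the two app arms; within-arm standardisation sets that to exactly 0 too. This part is algebra and needs no assumption about the questionnaire.

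The conclusion rests on two readings: that the reference is internal, which the text suggests but does not state, and that the Treatment Services Review is the satisfaction measure meant. Section 7.7 lists a patient satisfaction survey without naming it.

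The consequence is an uninformative stated answer to one part of a primary question. It is not a loss of data, and it does not affect the pain or engagement analyses.

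**What to change.** In sections 6.4.3 and 6.4.3.1, replace the z-score as the summary of satisfaction and acceptability. Report raw Treatment Services Review scores for each app arm and for both together, with 95% confidence intervals, and the difference between iCanCope-NF and iCanCope-NF +CM in raw units with its interval. Reporting by arm also shows each group separately whatever its size, which may be what the present sentence was after.

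If a z-score is kept as a supplement, state which mean and SD it uses and what it is for. The engagement analyses need no change on this account.

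The cost is a sentence or two of analysis wording, placed in both sections. It needs no new data, staff or patients.
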